##### 5.1.1 Outputs Presentation

###### 5.1.1.1 Tables Header

Since this is a single-arm study, all summary tables will be presented by Female, Male and Overall.

###### 5.1.1.2 Presentation of Gender Group

TFLs will be displayed using the following gender group label: Female, Male, Overall.

### 5.1.1.3 *Presentation of Visits / Timepoints*

Summaries by visit will be presented using visit number as collected in the eCRF.

Visits in the TFLs will be presented as follows and in that order:

Long Visit Name	Short Name
Screening (Visit 1)	Scr
Baseline (Visit 1)/ Baseline (Visit 2)	Bsl
Month 3 (Visit 3)	M3
Month 6 (Visit 4)	M6
Month 9 (Visit 5)	M9
Month 12 (Visit 6)	M12

### 5.1.2 *Descriptive Statistics*

All raw and derived variables will be listed and described using summary statistics. For categorical variables, summary statistics will be displayed using descriptive statistics by frequency count and percentages by category. The missing category will be presented if there is at least one missing category for at least one gender group. Except otherwise specified, participants with missing data will be included in the calculation of percentages. For quantitative variables, summary statistics will be displayed using descriptive statistics by number of observations, mean, standard deviation (SD), median, minimum and maximum. Missing data will be displayed.

### 5.1.3 *Baseline Value*

Unless otherwise specified, baseline is defined as the last non-missing measurement taken prior to first IMP administration (including unscheduled assessments). If the assessment time and/or IMP administration time is not collected, the assessment performed on the same day as the first IMP administration will be considered as baseline.

### 5.1.4 *Reference Start Date and Study Day*

Reference start date is defined as the day of the first IMP administration.

The day of the first IMP administration will be Day 1. Study day will be calculated as:

- The difference between the event date and the reference date plus one day, if the event is on or after the reference date.
- The difference between the event date and the reference date, if the date of event is prior to the reference date.

Study day will appear in any listings where an assessment date or event date appears.

In case of partial or missing event date, study day will appear missing while any associated durations will be presented based on the imputations described in appendix [A2](#).

## 5.2 *Disposition and Population*

Following disposition summaries and listings will be provided:

- Summary table with the number and percentages of treated participants per gender and site on the ITT population,
- Summary table for main study phase with the number and percentage of participants screened, screen failed, reason for screen failures, treated, completed the main study

phase, withdrawn the main study and reason for withdrawal and extension phase with the number and percentage of participants enrolled, treated, completed the extension phase, withdrawn the extension phase and reason for withdrawal, on the screened population,

- Summary table on duration of participant participation in the study. The definition of the duration of participant participation is from date of consent to the last study visit on the ITT population separately in main study phase and extension phase,
- Listing of dates of visit including duration of participant participation for the treated participants on the ITT population,
- Listing of screen failure participants on screened population,
- Listing of withdrawal participants on the ITT population.

Following population summaries and listings will be provided on the ITT population:

- Listing of participants violated inclusion criteria,
- Listing of participants fulfilled exclusion criteria,
- Summary of the number and percentage of participants in each analysis population by gender group, based on all treated participants with reasons for exclusion from each analysis population,
- Listing including flag for each analysis population and reason for exclusion from each population.

### **5.3 Protocol Deviations**

An exhaustive list of major protocol deviations that may occur during the course of the study and any action to be taken regarding exclusion of participants from the PPS population is defined in Protocol Deviation Assessment Plan. Major protocol deviations will be determined before database lock of the study, finalised during the data review meeting and documented in a separate document.

Following protocol deviation summary and listing will be provided on the ITT population:

- Number and percentage of participants with protocol deviations by deviation category separately in main study phase and extension phase (see DV section of Standard SDTM+ user guide),
- All protocol deviations will be listed with flags indicating if deviations are major or minor PDs separately in main study phase and extension phase,
- A separate listing for major protocol deviations will be displayed separately in main study phase and extension phase,

### **5.4 Demography and Other baseline characteristics**

All demographic and baseline characteristics summaries and listings will be provided for ITT, mITT, PPS and safety population.

Following summaries will be provided on:

- Demographic variables (age, ethnicity, sex)
- Other baseline characteristics (height, weight, BMI, pubertal stage, growth velocity, bone age, chronological age, the difference between bone age and chronological age),

- Baseline Disease characteristics (Time from initial diagnosis of CPP, GnRH-stimulated LH peak, GnRH-stimulated FSH peak, Basal LH, FSH, oestradiol levels and uterine length for girls, testosterone levels and testicular volume for boys).

Listings will also be provided for all the summaries listed above separately in main study phase and extension phase.

### 5.5 Medical history, non-drug therapies, medications and surgical procedures

Medical and surgical history, non-drug therapies and surgical procedures will be coded using the latest version of MedDRA in effect within IPSEN at the time of database lock. Medications will be coded using the latest version of WHO-Drug dictionary in effect within IPSEN at the time of database lock.

Medication, non-drug therapies and surgical procedures start and stop dates will be compared to the date of the first IMP administration to allow classification as either Prior only, Prior and Concomitant, or Concomitant only:

Prior (P)	Start and stop dates prior to the date of the first IMP administration.
Prior and Concomitant (PC)	Start date before the date of the first IMP administration and stop date on or after the date of the first IMP administration.
Concomitant (C)	Start date on or after the date of first IMP administration.

Summary tables on prior medications/non-drug therapies/surgical procedures will include “P” only, summary tables on concomitant medications/non-drug therapies/surgical procedures will include “C” and “PC”.

See detailed rules in appendix [A2](#) for classification of prior and concomitant medication/non-drug therapies, surgical procedures in case of partial/missing date.

The therapeutic class will correspond to the second level of ATC code, that is, corresponding to the first 3 figures.

Following summaries, presenting count and percentages of participants will be provided on the ITT population:

- Medical and surgical history by primary system organ class (SOC) and preferred term (PT),
- Prior medications (P) for the study indication by ATC class (ATC level 2) and preferred Name PN,
- Concomitant medications (PC, C) for the study indication by ATC class (ATC level 2) and preferred Name PN,
- Prior non-drug therapies (P) by primary SOC and PT,
- Concomitant non-drug therapies (PC, C) by primary SOC and PT,
- Prior surgical procedures (P) by primary SOC and PT,
- Concomitant surgical procedures (PC, C) by primary SOC and PT,

Listings will be provided for all the summaries listed above. These listings should include a flag indicating the category (P, PC, C) as described in the table above.

A prohibited medication listing be provided including the following drug:

Oestradiol, Testosterone, GnRH analogues (other than triptorelin 3-month formulation), medroxyprogesterone acetate, growth hormone or IGF-1, systemic or inhaled steroids (mild topical steroids are permitted), anticoagulants (heparin and coumarine derivatives).

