3.2.3 Safety Endpoints and Evaluations

Safety and tolerability will be assessed throughout the study by evaluating treatment-emergent adverse events (TEAEs), including local tolerability and injection site-related reactions), clinical laboratory test results, vital signs measurements, physical examination results and changes from baseline in concomitant medication usage. Safety parameters will be monitored at various timepoints from the time the participant provides informed consent to the end of the study, as follows:

- Incidence of TEAEs throughout the study, including local tolerability
- Change in clinical safety laboratory (blood biochemistry, haematology and urinalysis) parameters at Month 3 and 6
- Change in physical examination and vital signs (blood pressure and heart rate) measurements at each visit.

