6.3 Concomitant Medication/Therapy

Any prior or concomitant therapy or medication given to a participant within 2 months before triptorelin administration or during triptorelin administration will be recorded on the eCRF. Dose and generic name or trade name will be indicated.

The following concomitant medications/procedures are not permitted during this study:

- Any treatment or procedure with a definitive or potential effect on the metabolism or secretion of gonadotropins (LH or FSH) or sex steroids (oestradiol and/or testosterone) will be considered as a protocol violation;
- All drugs mentioned as prohibited in the exclusion criteria remain prohibited during the study period: GnRH analogues (other than triptorelin 3-month formulation), medroxyprogesterone acetate, growth hormone or IGF-1, systemic or inhaled steroids (mild topical steroids are permitted), anticoagulants (heparin and coumarine derivatives).
- Any concurrent investigational agent or procedure.

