A TEAE is defined as any AE that occurs during the active phase of the study (between the start date of the treatment and the end of study treatment) if:

- It was not present prior to receiving the first dose of triptorelin, or
- It was present prior to receiving the first dose of triptorelin but the grade increased or became serious during the active phase of the study, or
- It was present prior to receiving the first dose of triptorelin, the grade/seriousness is the same but the causality changed to “related” during the active phase of the study.

All TEAEs will be flagged in the AE listings.

Summary incidence tables will be provided, classified by SOC, PT and associated NCI-CTCAE worst grade. In the event of multiple occurrences of the same AEs being reported for the same participant, the maximum intensity (Grade 5 > Grade 4 > Grade 3 > Grade 2 > Grade 1 > missing > not applicable) will be chosen. All AEs will be collected up to the EOS visit (see [Table 1](#) for schedule), or EOEP visit for those enrolled in the extension phase.

Concomitant medication will be coded by using World Health Organization Drug Dictionary (WHO-DD) version (current version in use at the start of the study) and will be summarised with the number and percentage of participants receiving concomitant medication by drug class and preferred drug name.

Haematological and biochemical toxicities will be recorded and graded according to the NCI-CTCAE criteria, where available. The NCI-CTCAE Grades 3 and 4 haematology and biochemistry variables will be listed by participant and by visit.

Actual values and changes from Baseline in clinical laboratory tests, physical examinations and vital signs will be summarised using descriptive statistics at each visit. For laboratory data, abnormal values will be flagged in the data listings and a list of clinically significant abnormal values will be presented. Shift tables using the worst on-treatment grade will be presented for the number and percentage of participants with NCI-CTCAE grades.

11.4.7 *Efficacy and Safety Evaluations (Extension Phase)*

A separate analysis on efficacy and safety endpoints will be performed considering the extension phase duration, a period of an additional 6 months, lasting until the End of Extension Phase Visit at Month 12.

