**2.6 Change from Statistical Section of the Protocol**

There is no change in SAP from statistical section of the protocol.

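### SAP 5.5 confines its medication tables to drugs for central precocious puberty, while the protocol summarises all concomitant medication and the SAP declares no change

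*SAP*

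**What the plan says.** SAP 5.5 sorts medications, non-drug therapies and surgical procedures by timing relative to the first injection: prior, prior and concomitant, or concomitant. It then lists the summaries to be produced on the ITT population. Two of these concern medications: "Prior medications (P) for the study indication by ATC class (ATC level 2) and preferred Name PN" and "Concomitant medications (PC, C) for the study indication by ATC class (ATC level 2) and preferred Name PN". The other items in the list carry no indication limit, for example "Concomitant non-drug therapies (PC, C) by primary SOC and PT". On listings, the section says "Listings will be provided for all the summaries listed above". It also asks for a separate listing of prohibited drugs.

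The protocol is broader. Section 6.3 has any prior or concomitant therapy or medication given "within 2 months before triptorelin administration or during triptorelin administration will be recorded on the eCRF". Section 11.4.6, on the safety evaluation, says that concomitant medication "will be summarised with the number and percentage of participants receiving concomitant medication by drug class and preferred drug name". Section 11.4.1 includes prior and concomitant medications among the data described for the ITT, mITT, PP and Safety populations, again without an indication limit. The opening sentence of section 3.2.3 names "changes from baseline in concomitant medication usage" among the things by which safety is evaluated.

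SAP 2.6 states: "There is no change in SAP from statistical section of the protocol".

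**The concern.** The protocol collects every medication and promises a summary of all concomitant use as part of the safety evaluation. The SAP's explicit list of outputs keeps only drugs given for the disease under study. In this trial those are largely the drugs that a child may not take.

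A programmer working from SAP 5.5 would apply the filter. The resulting table would leave out medicines for intercurrent illness, medicines given to treat adverse events, and permitted medicines that a reader might want to weigh against growth or hormone results. The data would sit in the database, but the report would lack the tabulation that the protocol describes. Because SAP 2.6 says that nothing changed, nobody comparing the two documents would be alerted.

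**Working it through.** No arithmetic applies. The check is a comparison of scope.

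**1. What is collected.** Protocol 6.3: any medication, from 2 months before dosing and during treatment. There is no restriction by indication.

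**2. What each document tabulates.**

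| Source | Medications covered | Population |
|---|---|---|
| Protocol 11.4.1 | Prior and concomitant, no indication limit | ITT, mITT, PP, Safety |
| Protocol 11.4.6 | Concomitant, by class and preferred name, no indication limit | Safety |
| SAP 5.5 | Prior and concomitant, study indication only | ITT |

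**3. Whether the limit is general or specific.** SAP 5.5 lists seven summaries. Only the two medication items carry the limit; medical and surgical history, the two non-drug therapy items and the two surgical items do not. Read literally, the limit is specific to medications. It may be wording carried over from a template.

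**4. What could enter the limited table.**
- At entry: protocol 4.2 excludes children with prior or current GnRH agonist, medroxyprogesterone acetate, growth hormone or IGF-1 therapy.
- On study: protocol 6.3 prohibits GnRH analogues other than the study drug, the other agents just named, and any treatment with a definite or potential effect on gonadotropins or sex steroids.
- Alternatives: protocol 1.1 says that no effective option exists for this condition other than prolonged-release synthetic GnRH.

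With the study drug set aside, what remains for the concomitant table is mainly protocol violations. The prior table could also hold an earlier treatment for the condition that is not on the exclusion list.

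**5. Whether another SAP output fills the gap.** SAP 5.8 specifies tables for exposure, adverse events, local tolerability, laboratory data, vital signs and physical examination, but none for concomitant medication. The prohibited-drug listing in 5.5 covers named drugs only. It does not reach the protocol's wider class of treatments with a potential hormonal effect, its ban on concurrent investigational agents, or any permitted medicine.

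**6. Whether the departure is declared.** Protocol section 11 allows the SAP to change the plan, so a narrower table is not forbidden. SAP 2.6, however, says that there is no change. That statement and the limit in 5.5 cannot both stand.

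**The case against.** The strongest reply is that the SAP's general rules already cover all medications. SAP 5.1.2 says that raw and derived variables will be listed and summarised. SAP 5.8.1 says that safety data go into participant listings, and the protocol treats concomitant medication as part of the safety evaluation. Within 5.5, the sentence on which timing categories enter the concomitant tables has no indication limit. The table shells are a separate document and may be correct.

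Part of this stands. A reader might infer from the sentence tying listings to the preceding summaries that the full medication listing is lost. The documents do not support so firm a conclusion, because 5.1.2 and 5.8.1 plausibly preserve one; the listing's scope is ambiguous. The reply does not restore the table. None of those general statements names an all-medication summary, and the timing sentence sets categories, not content. The explicit bullets are what would be programmed.

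The reply is also right that the consequences are partly covered. Adverse events are tabulated and listed whatever drug treated them, prohibited drugs have their own listing, and protocol deviations are tabulated and listed. What is left uncovered is a frequency table of permitted medicines in a single-arm descriptive study of 32 children.

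**Conclusion.** The point holds as a minor, undeclared inconsistency. SAP 5.5 is narrower than protocol 11.4.1 and 11.4.6, no other section supplies the missing table, and SAP 2.6 says that nothing changed. No estimate or confidence interval for efficacy is affected.

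Two stronger readings are tempting and should not be drawn:
- **A count close to 0 of the 32 children.** The direction follows from the exclusion and prohibition rules, but the documents give no medication counts, so no figure can be attached. Setting the concomitant table against everything recorded from 2 months before dosing would also be unfair, since that look-back includes drugs stopped before the first injection, which the SAP classes as prior.
- **The loss of a safety endpoint.** Change in concomitant medication use appears only in the introductory sentence of protocol 3.2.3. It is not among the three safety endpoints bulleted after it, nor among those in the synopsis.

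The conclusion rests on reading the SAP 5.5 bullets literally and on the table shells, which are not available here, following them.

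**What to change.** In SAP 5.5:
- Remove the study-indication qualifier from both medication bullets, or keep those tables and add all-medication tables, prior and concomitant, by ATC level 2 and preferred name.
- State that the medication listing covers every medication recorded on the eCRF.
- Align the population. The section uses ITT only, so add at least the Safety population, and either add mITT and PP as in protocol 11.4.1 or say why they are dropped.

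If the narrower tables are intended, declare and justify the departure in SAP 2.6 instead.

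The cost is a few words in the SAP, a check of the shells, and running the same program without a filter and on one further population. No new data are needed.

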## 5.6 Compliance

Compliance will be present separately in main study phase and extension phase,

Compliance with study treatment will be presented as the number and proportion of patients who received the two IMP injections. A listing of treatment compliance will be provided.

## 5.7 Efficacy (Main Study Phase)

### 5.7.1 General Considerations

The analysis sets for the primary and secondary efficacy endpoints will be the mITT population.

Supportive analysis of the primary efficacy endpoints will be based on the ITT and the PPS populations. Supportive analysis of the secondary analyses may be performed on the PPS population.

A listing of all efficacy data (raw and derived) should be provided (see listing detail conventions in Appendix [A4](#)). Descriptive statistics will be provided for all endpoints.

#### 5.7.1.1 Significance Testing and Estimations

The statistical analysis of efficacy is only descriptive therefore no formal statistical significance testing will be performed.

#### 5.7.1.2 Statistical/analytical issues

##### Adjustments for Country/Centre Effect

Descriptive analysis will be carried out to evaluate any possible centre effect.

##### Handling of Dropouts or Missing Data

A NRI method will be used for missing LH response and FSH response at month 3 or month 6. For any missing value of LH response and FSH response at month 3 or month 6, a Non-response value will be imputed.

##### Interim Analyses and Data Monitoring

No interim analysis will be performed.

##### Multicentre Studies

No by-centre displays or adjustments for centre are planned for this study.

##### Multiple Comparisons/Multiplicity

Since no formal hypothesis test will be performed in this study, no multiple testing will be performed in this study

Use of an "Efficacy Subset" of Participants

No Efficacy subset is planned in this study.

Examination of Subgroups

No subgroup analysis is planned.

**5.7.2 Analysis of Primary Efficacy Endpoint****5.7.2.1 Endpoint**

LH Response: defined as a peak LH  $\leq 3$  IU/L after intravenous (i.v.) gonadotropin-releasing hormone (GnRH) stimulation in Chinese children with central precocious puberty (CPP).

**5.7.2.2 Primary Analysis**

For the primary efficacy endpoint, the summary statistics of number and percentage of participants and the exact two-sided 90% confidence interval (CI) for a binomial proportion will be computed by SAS® using the exact binomial distributions on the mITT.

The SAS code to be used could be presented in Appendix A1.

A listing will be provided including all participants with missing values for the primary endpoint. For these participants, the listing will provide all observed data related to the primary endpoint i.e. all measurements recorded prior to the missing value, any measurements recorded after the missing value, important baseline characteristics, the reason for study discontinuation and the timing of study discontinuation. The listing will also provide the imputed value(s) (if applicable) used in the primary analysis and any sensitivity analyses.

**5.7.2.3 Sensitivity Analysis**

Sensitivity analyses will be conducted to further explore the primary efficacy endpoint with the same statistical method using NRI method on the ITT set.

A PPS population will also be used to explore the primary efficacy endpoint with the same statistical method.

